We were approved by PCORI to modify of our research protocol to expand our inclusion criteria from Parkinson's disease (PD) to also include the closely related neurodegenerative conditions of multiple systems atrophy (MSA), corticobasal degeneration (CBD), progressive supranuclear palsy (PSP) and Lewy Body Dementia (LBD). These disorders are collectively referred to as Parkinson-plus syndromes or atypical parkinsonian disorders (APD) and are related to PD in terms of both clinical manifestations and pathology.⁹ Current standards of care for APD patients are very similar to PD patients, and include care from a neurologist and PCP as well as trials of the same medications used to treat PD. These patients suffer from many of the same complications as PD patients (e.g. falls, dysphagia, dementia, depression) and tend to have less response to motor treatments (e.g. levodopa) and faster progression. Although these conditions are individually rare, collectively they account for approximately 15% of all parkinsonism and, because they are largely untreatable and more rapidly progressive than PD, may have a higher proportion of patients and caregivers with high palliative care needs.^{30, 31} All of the palliative care clinics involved in this study see APD patients which makes the question of clinical effectiveness equally important for APD patients, caregivers and clinicians as it is for PD.

From a practical standpoint, recruitment has been more challenging than initially anticipated. We have had higher than expected rates of refusal due to time commitment and logistical challenges among patients. We have also had many potential participants refuse to agree to be randomized as they feel they have high needs and do not want to take the 50% chance of being randomized to usual care. Although this is the first trial of a palliative care intervention in Parkinson's disease (PD), similar issues have been described in palliative care trials for other conditions.^{32, 33} Expansion of our recruitment criteria to include APD patients is anticipated to improve our recruitment numbers and may account for one-third of our final sample. We have already had several potential participants excluded because of having an undiagnosed APD and have had requests from referring clinicians to see their APD patients in the study.

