From a theoretical standpoint there are several reasons why the inclusion of APD patients is attractive. First, regarding palliative care services there are no significant differences in the care our palliative care clinics provide to APD versus PD patients in terms of symptomatic needs (e.g. dementia, depression, dysphagia), goals of care, caregiver support, psychosocial issues or spiritual care.³¹ Second, there is a paucity of clinical therapeutic research to guide care for patients with APD and this study will help fill this gap and encourage other investigators to include this patient population.³⁴ Finally, the inclusion of APD patients is consistent with PCORI and palliative care principles to move towards patient-centered care based on symptoms or other shared challenges (e.g. elderly multiple comorbidities) as opposed to specific diagnoses and there are other clinical researchers in neurology and palliative care moving in this direction.³⁵

INNOVATION

Although growing evidence supports palliative models for several chronic illnesses there is scant evidence and no randomized trials supporting this approach in PD.^{12, 19, 36, 37} This proposal will conduct the first randomized trial of outpatient palliative care for PD. While this trial builds on prior palliative trials our approach is innovative in its application of these methods to the specific needs of PD. *Specifically, our Aims will be the first studies to:*

- 1) Test the impact of outpatient palliative care in PD on patient QOL and caregiver burden in a randomized controlled trial. The intervention is based on our collective experience in providing palliative care for PD. Our study sites represent the first clinics and longest experience with this work in North America. Clinical trial results for other illnesses do not directly translate to PD due to unique aspects of PD such as the long duration of illness (10-20 years) and variable combination of motor and nonmotor symptoms.
- 2) Use the recently developed Needs Assessment Tool - Parkinson's Disease to provide standard and reproducible screening of high-risk patients. This instrument was modified for PD by Drs. [name] and [name] with input from [name] (PI) from the Palliative Care Needs Assessment Tool.³⁸

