Participants: *Inclusion Criteria:* Patients must be fluent English Speakers, over age 40 and meet UK Brain Bank criteria for a diagnosis of probable PD⁴⁶ or standard criteria for progressive supranuclear palsy (PSP),⁴⁷ corticobasal degeneration (CBD),⁴⁸ multiple systems atrophy (MSA),⁴⁹ or Lewy Body Dementia (LBD).⁵⁰ Although PD may be seen in individuals under age 40, it is more frequently related to specific genes and may display different clinical features than typical idiopathic PD. Patients must be at high risk for poor outcomes as identified by the Palliative Care Needs Assessment Tool (PC-NAT)³⁸ modified for PD which screens patients on the basis of social factors (e.g. presence of caregiver), disease severity, and symptom burden. Every effort

will be made to allow inclusion of patients with dementia and cognitive impairment per NIH guidelines⁵¹ (see **Human Subjects** section for details on consenting process).

Caregivers, when present, will be identified by asking the patient: "Could you please tell us the one person who helps you the most with your PD outside of clinic?" For patients with severe dementia, family caregivers may be self-identified and may be included even if the patient has communication limitations in order to obtain data relevant to these highly vulnerable and underrepresented patients. We anticipate 90% of patients will have caregivers present based on our clinical experience and have performed separate power calculations for caregiver outcomes, including with lower percentages of complete dyads. Notably, our primary patient outcome measure has been validated in patients with dementia and with proxy caregiver reporting.⁵²

Exclusion Criteria: Patients will be excluded if any of the following are present: 1) Immediate and urgent palliative care needs (these patients will not be randomized and will be offered appropriate services immediately); 2) Unable or unwilling to commit to study procedures including randomization, study visits or the addition of a neurologist to their care team if in the usual care arm and not currently seeing a neurologist; 3) Presence of additional chronic medical illnesses which may require palliative services (e.g. metastatic cancer); or 4) Already receiving palliative care and/or hospice services. We have purposefully kept our inclusion/exclusion criteria broad to allow for greater generalizability of results and to ensure inclusion of potentially underrepresented and understudied subgroups.

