Randomization: Individual patients and patient-caregiver dyads will be randomized in a 1:1 fashion to either: 1) Usual care defined as including both a PCP and neurologist; or 2) Usual care augmented by an outpatient interdisciplinary palliative care team. Randomization will be stratified by site, presence of caregiver, presence of dementia using Movement Disorders Society Guidelines for PD-related dementia and the Montreal Cognitive Assessment,^{53, 54} and performed in balanced blocks to minimize potential biases.

Description of the Intervention and Comparator Arms: Comparator: Usual care will consist of care from the patient's primary care physician (PCP) and a neurologist. We consider this the current standard on the basis of evidence showing that care with a neurologist results in better outcomes (e.g. falls, mortality) than care with a PCP alone.⁶ For patients without a neurologist, we will arrange appointments with a neurologist covered by their insurance or a patient assistance program. Patients will be asked to see their neurologist at least every 3 months to match the frequency of visits in the intervention arm and may see their PCP at their typical frequency. Data collection for those in the Usual care arm could occur in person, over the phone, using mailed or electronic survey distribution, or via telemedicine. To ensure treatment fidelity, investigators will not serve as neurologists in the comparator arm.

Intervention Arm: Out intervention will consist of Usual Care plus the addition of an outpatient interdisciplinary palliative care team. Palliative care visits will be performed in person (or telemedicine if needed for rural areas and/or limited transportation) every 3 months and will include consultation with all team members. In addition, visits will be supplemented by optional phone calls one week after each visit to confirm understanding of team recommendations and at 6 weeks to check-in with patient and caregiver. Data collection for those in the Intervention arm could occur in person, over the phone, using mailed or electronic survey distribution, or via telemedicine. Patients and caregivers may also contact the team as needed. Summaries of visits will be sent to the patient, caregiver, PCP and neurologist. The palliative team will enact changes related to core palliative care issues (Table 1) and make suggestions for care outside of palliative care issues to be sent to the patients' Usual Care team.

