Unified Parkinson Disease Rating Scale ⁴¹	Patient Motor symptom Severity (motor exam only)
Montreal Cognitive Assessment (MOCA) ^{46, 56}	Patient Cognitive Status
Hoehn and Yahr Scale ⁴⁴	Patient Disease Stage (baseline visit only)
Charlson Comorbidity Index ^{61, 66}	Medical Comorbidities (baseline visit only)

Statistical Analysis: The main objective of the study is to determine the comparative effectiveness of interdisciplinary outpatient palliative care versus usual care with a neurologist for PD regarding effects on patient QOL and caregiver burden. The primary outcome variables will be the QOL-AD and the ZBI.^{40, 55} Secondary outcomes (see **Table 2**) include scales for symptom burden, mood, and spiritual wellbeing. Controlling covariates will include gender, age, disease severity (measured continuously using the Unified Parkinson Disease Rating Scale⁶⁷), cognitive dysfunction (measured continuously using the Montreal Cognitive Assessment⁶⁸), and baseline depression (measured continuously using the HADS Depression Subscale⁶⁴). The explanatory variables will be checked for randomization and multicollinearity. Successful randomization should minimize covariate imbalances between groups, but including them in the model can adjust for lingering confounding effects and account for variance in the outcome variable.

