The outcomes will be modeled with mixed regression model analysis, with correlation for repeated measures, at baseline and at 3, 6, 9, and 12 months. The empirical covariance estimator may be used to safeguard against model misspecification. The models will control for time, interaction between treatment and time, and potential baseline confounders, including gender, age, depression, and disease severity. The default model will have linear time trajectories for each treatment group, and linear functions for baseline controlling covariates. The linearity assumptions will be checked. Non-linear functions could be approximated with piecewise linear functions or transforms. The main contrasts will be the difference in areas under the fixed effect change from baseline curves for the palliative and treatment control groups, and the mean difference in change between 6 months and baseline between the groups. Secondary tests will be conducted for the mean difference in change from baseline between the groups at the 3, 9, and 12-month time points. The contrasts, controlled for all covariates, will be tested for significance using T-tests and F-tests, with an alpha level of 0.05. The effect estimates, 95% confidence intervals, and p values will be reported. In the process, the interaction between time and treatment will be tested. If the time trajectories are linear, then all tests are stochastically equivalent to the time by treatment interaction test with one parameter. Binary outcomes and count outcomes will be analyzed with logistic regression and Poisson regression respectively. Generalized mixed models will account for repeated measures. We plan to perform subgroup analyses for patients with dementia, severe disease, and depression and may perform exploratory subgroup analyses depending on primary results.

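### Two of the three randomisation stratifiers are missing from the Aim 1 covariate lists, and PD/APD diagnosis is in no analysis list: a minor gap that costs little and does not bias the primary contrast

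*Combined protocol and SAP*

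**What the plan says.** **Strata.** The Randomization paragraph of Aim 1 states: "Randomization will be stratified by site, presence of caregiver, presence of dementia using Movement Disorders Society Guidelines". The Aim 1 Statistical Analysis gives two covariate lists. The first opens "Controlling covariates will include gender, age, disease severity (measured continuously using the Unified Parkinson Disease Rating Scale" and adds MoCA and baseline depression. The second, which is open-ended, has gender, age, depression and disease severity, without MoCA. Neither has site or caregiver presence. The Aim 2 cost model does adjust for site.

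**Diagnosis.** The Significance section says that the inclusion of APD "is anticipated to improve our recruitment numbers and may account for one-third of our final sample", that APD progresses faster than PD, and that seeing APD patients in the study clinics "makes the question of clinical effectiveness equally important for APD patients, caregivers and clinicians as it is for PD". The same section defends pooling: "there are no significant differences in the care our palliative care clinics provide to APD versus PD patients".

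Diagnosis is in neither Aim 1 covariate list. The subgroup sentence reads: "We plan to perform subgroup analyses for patients with dementia, severe disease, and depression and may perform exploratory subgroup analyses depending on primary results". The Aim 3 Predictor Variables list includes caregiver presence but not diagnosis. It does allow other variables, and item 4 of Potential Problems promises subgroup analyses through Aim 3.

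**The concern.** A model normally carries the factors that restricted the randomisation. If they are left out, the standard error still contains between-stratum variance that the blocked allocation has already balanced, so the test can be slightly conservative. The plan allows covariates to be brought in after a baseline check, but that would be a choice made on the data.

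Eligibility was widened to APD, but the lists of covariates, subgroups and modifiers do not name diagnosis. An APD analysis remains possible. However, the Aim 1 route depends on the primary result and the Aim 3 route names no diagnosis variable, so nothing commits the trial to reporting the APD effect. What is at stake is a little precision in the primary test, and whether an APD result can be shown to have been planned.

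**Working it through.** **Inputs.** From Aim 1, Sample Size and Power Considerations: 125 per arm, compound symmetry with correlation 0.5, an effect of 0.36 SD. From Significance: an APD share of one-third, so 125/3 = 41.7, about 42 per arm. Alpha 0.05 is taken as two-sided (assumption). For 90% power the z sum is 1.960 + 1.2816 = 3.2415. Data are complete unless stated.

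**1. Reproduce the plan's figures.** With n per arm and a common intercept, the variance of the 6-month effect is k/n in SD units.
- Piecewise model, 6-month contrast: k = 2(1 − 0.5²) = 1.5. Detectable effect 3.2415·√(1.5/n) = 0.355, 0.496 and 0.418 at n = 125, 64 and 90; stated 36%, 50% and 42%.
- Piecewise model, area contrast divided by 12 months: visit weights 0.25, 0.25, 0.25, 0.125; after baseline adjustment the variance is 0.75 and the covariance 0.25. So k = 2(0.5·0.2031 + 0.25·0.875²) = 0.586. At n = 125, 3.2415·√(0.586/125) = 0.222; stated 22.5%. At n = 63, 0.313; stated 32% (Aim 3 power section).
- Linear slopes over five visits: k = 36·2/240 = 0.3, where 240 = 2·270 − 30²/3 is the information on each arm's slope per patient. At n = 63, 3.2415·√(0.3/63) = 0.224; stated 23%.

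**2. Omitted strata, 6-month contrast.** Suppose the strata explain a constant share R² of variance (assumed; no figure in the documents).
- Without strata the model reports variance 0.75, while the true value is 0.75 − 0.25R².
- With strata it is (1 − R²) − (0.5 − R²)²/(1 − R²).
- Size without strata = 2Φ(−1.96·√(0.75/(0.75 − 0.25R²))).

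| R² | true size without | power without | power with | loss (points) |
|---|---|---|---|---|
| 5% | 4.8% | 90.9% | 91.2% | 0.3 |
| 10% | 4.6% | 91.1% | 91.8% | 0.6 |
| 20% | 4.2% | 91.5% | 93.0% | 1.4 |

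Where MoCA stays in the model, these losses are upper figures. In the linear model with separate group intercepts, a constant stratum effect cancels from the slope difference. The SE at 125 per arm is √(0.4/125) = 0.0566 with or without strata (k = 36·2/180 = 0.4), so the loss is zero.

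**3. Adjusting for diagnosis, 6-month contrast.** Assume APD declines d SD more than PD by 6 months. Residual variance is 0.75 − d²·p(1 − p).
- p = 1/3: 0.7411 (d = 0.2) and 0.6944 (d = 0.5). Power rises from 90.8% to 91.1% and 92.7%.
- p = 15%, the plan's figure for the APD share of all parkinsonism: power 90.9% and 91.9%.

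These are upper bounds, because UPDRS and MoCA would share variance with diagnosis.

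**4. Bias.**
- In 4,000 simulated stratified trials with no true effect, the mean estimate was −0.001 SD (Monte Carlo SE 0.002) both with and without strata and diagnosis. Rejection was 3.9% without them and 5.2% with them, under assumed prognostic effects.
- With more dropout in APD but the same in both arms, a true 0.36 SD was estimated as 0.356 without diagnosis and 0.358 with it.
- With assumed APD dropout per visit of 0.20 in usual care against 0.06 elsewhere, leaving out diagnosis shifted the contrast by about −0.03 SD. Adding diagnosis and diagnosis-by-time removed the shift when the effect was common to both groups.

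**5. Precision for APD, QOL-AD.** SE = √(k/41.7); power is at a true 0.36 SD. For the PD–APD difference, SE = √(k(1/41.7 + 1/83.3)).

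| Contrast | SE | 95% half-width, APD | power | half-width, difference |
|---|---|---|---|---|
| Linear slopes (default) | 0.085 | 0.17 SD | 99% | 0.20 SD |
| Piecewise, area | 0.119 | 0.23 SD | 86% | 0.28 SD |
| Piecewise, 6 months | 0.190 | 0.37 SD | 48% | 0.46 SD |

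Scaling the plan's own 23% and 32% by √(63/42) gives APD half-widths of 0.17 and 0.24 SD, with power of about 98% and 85%. Dropout or non-linear trajectories would worsen every row. For ZBI, 110 dyads per arm widen the intervals by √(125/110) = 1.07.

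**The case against.** The strongest reply is that little is lost and much is already covered. Pooling PD and APD is deliberate: Aim 1 is posed for both together, and the Significance section argues from shared needs and shared clinic care. The statement that the question matters equally for APD supports inclusion; it does not promise a separate estimate. Unlisted Aim 1 subgroups are already labelled exploratory, so readers are warned. Dementia is a planned subgroup, MoCA is a covariate and caregiver presence is an Aim 3a predictor. The one-third share is a recruitment expectation. All of this stands, and it keeps the point minor. It does not put site or caregiver presence into the Aim 1 models, and it does not commit the plan to an APD estimate.

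Two stronger readings are tempting.

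A reader might infer that leaving out diagnosis confounds the primary comparison. Randomisation rules that out with complete data, and the documents give no dropout figures by arm and diagnosis that would reopen it.

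A reader might also infer that an APD estimate is hopeless, from 48% power, or that it would be inflated: reporting it only when p < 0.05 would give a mean of 0.52 SD for a true 0.36, or 1.4 times. Both figures belong only to the piecewise 6-month contrast. Under the default linear model power is about 98–99% and the inflation about 1.01 times.

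**Conclusion.** The gap is real and minor. Two of three stratifiers are absent from the Aim 1 lists, the third enters only as continuous MoCA in one list, and diagnosis is named nowhere as a covariate, planned subgroup or modifier.

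The primary contrast stays unbiased with complete data, or when dropout does not depend jointly on arm and diagnosis. The cost of omitting the strata runs from zero (separate group intercepts) to 1.4 power points (common-intercept 6-month contrast, strata explaining an assumed 20% of variance), with a test that errs on the conservative side. Adjusting for diagnosis adds at most about 2 points.

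The more useful gain is a pre-named PD/APD estimate. Its precision depends mainly on whether the linear model holds.

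**What to change.** (a) In the Aim 1 models, add site and the dementia stratum as fixed effects, and caregiver presence for QOL-AD only, since it is essentially constant in the ZBI analysis.

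(b) Optionally, add diagnosis and diagnosis-by-time for precision. The time term is needed because the difference the plan describes is one of progression.

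(c) Name PD/APD diagnosis in the Aim 3 Predictor Variables list. The Aim 3a analysis rule for categorical modifiers then already calls for the effect at each level. State that the PD effect, the APD effect and their difference will be reported with 95% confidence intervals whatever the primary result, as secondary estimation and not as a confirmatory test.

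The cost is SAP wording and a few degrees of freedom. Diagnosis is established at eligibility and the strata at randomisation, so no new data are needed. The change should be made before outcomes are examined by arm.

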Study Settings/Recruitment: Participants will be *identified and recruited* for this study through three institutions: 1) The University of Colorado Denver (UCD); 2) The University of California San Francisco (UCSF); and 3) The University of Alberta. The institutions represent the 3 first outpatient palliative care clinics for PD in North America and were chosen based on their collective experience. Recruitment at each institution will occur through three main venues: 1) Referral from investigators' clinics or their colleagues at primary study sites (tertiary care academic clinics and community health clinics); 2) Referral from community physicians with ongoing working relationships with site institutions and investigators; and 3) Self-referral by patients who learn of the study through community organizations, talks, advertisements or websites (e.g. clinicaltrials.gov; foxttrialfinder). To ensure inclusion of community and rural participants, each study site has partnered with community neurologists and regional patient organizations which provide services to rural patients. Study sites also provide services through inner city clinics serving indigent populations and the two US sites are partnered with Veterans Affairs Medical Centers. Efforts made to *retain* participants will include: reimbursement for travel and expenses; providing baseline and/or follow-up study visits at participant homes or by telehealth for patients and/or caregivers with health, mobility, or transportation issues; incorporation of telemedicine approaches as needed for rural and other locations; mailed updates of study progress to participants; incorporation of feedback from participants regarding study procedures; and a welcome letter referring to participants as important members of the study team. A caregiver will be consented/enrolled for each participant who has one available. In some cases, the consent process will occur in a telehealth (phone or video) meeting with the participant and will be performed by study personnel. The patient/caregiver/LAR will have a copy of the consent form and the UCD study coordinator will go through the consent process with them via phone or video, just as they would in person. Patient/caregiver/LAR will give verbal consent.

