Item non-response for the scales will be dealt with using the half rule, or specific scale instructions when available (e.g. QOL-AD⁵⁷). The half rule is the standard method for completing validated scales with missing items when the items are not hierarchical and generally has better performance than more complex imputation methods.⁶⁹ Descriptive statistics will be compiled for missing scales and assessed for patterns. Logistic regression for missingness will be used to demonstrate its dependency on variables. The initial analysis will use the maximum likelihood for all available data for a response variable when data exists for all explanatory variables. In mixed models correlation on repeated outcomes provides some information on the times with missing outcome values. The data will be assumed missing at random. As a sensitivity analysis, joint models will combine the longitudinal outcomes of patient and caregiver proxy reports on the QOL-AD and use their correlations to provide additional values if a subset of the outcomes are missing. Finally, joint models for the longitudinal QOL scale outcomes and the time to drop out will be fit to incorporate drop out information. Even if outcomes for one scale are not missing at random conditional on the observed data, measurements on other scales at the time, or time to drop out, can serve as proxies. Models for different outcomes and time to drop out will be joined through shared covariance structures and/or shared random effects.

The functions in the regression model will be checked for linearity. Piecewise linear functions or transforms can be used to approximate non-linearities. Crossover of group assignment will be treated in different ways and the results will be compared. The primary analysis will use intent-to-treat, but analysis according to actual treatment, with time varying covariates, and adherers only will also be considered. Results

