* administered by clinician – inclusion/exclusion form, NAT – PD, MOCA, MDS UPDRS Motor Subscale, Hoehn and Yahr Staging, History, UK Brain Bank Clinical Staging, Patient Performance Scale and Charlson Comorbidity Index

ΩΩ administered by coordinator – consent, UBACC, QOL – AD, PROMIS – 29, Medications, Demographics and Health Utilization

ü self-administered (patient) - PDQ – 39, ESAS –PD, FACIT – SF, PG -12 and PROMIS -29

β self- administered (caregiver) - Zarit Burden of Care Instrument, EQ-5D

After review of consent with subject, UBACC then should be administered next by the coordinator to see if subject has the capacity to consent prior to signing consent.

No study procedures should be completed prior to the consent process.

QOL – AD and Zarit Burden of Care Instrument (ZBI) [care giver] if applicable, should be administered first prior to any other study procedures.

Please note, CGI will be administered by coordinator at 3 and 9 month visit (omit questions 2C at 3 and 9 month visits) and at 6 and 12 month visit it will be administered by the clinician.

6 week assessment after every scheduled visit will be done by phone.

3, 6, 9 and 12 month visit, only capture medication changes.

Data collection for all study visits can be done by phone, online survey, via telehealth, or in person.

Time windows for study visits and data collections are as follows:

- The 3, 6, 9, and 12-month visits should occur within +/- 4 weeks of scheduled date.
- The one week follow-up phone call should occur within 1 week of scheduled date.
- The six week follow-up phone call should occur within 2 weeks of scheduled date.
- The six-week health care utilization survey call should occur within 2 weeks of scheduled date.

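### The initial Aim 1 analysis excludes any randomised participant with a wholly missing baseline covariate, and the plan gives no remedy

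*Combined protocol and SAP*

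**What the plan says.** All references are to the combined protocol and SAP.

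- **Rule for missing covariates** (Aim 1, Statistical Analysis): "The initial analysis will use the maximum likelihood for all available data for a response variable when data exists for all explanatory variables". No other analysis is named as primary, so I read this as the primary one.
- **Covariates** (same section): gender and age, plus "disease severity (measured continuously using the Unified Parkinson Disease Rating Scale", "cognitive dysfunction (measured continuously using the Montreal Cognitive Assessment" and "baseline depression (measured continuously using the HADS Depression Subscale". Table 2 limits the UPDRS to the motor examination. The next paragraph, on the mixed model, gives a shorter, non-exhaustive list that repeats depression and disease severity but omits cognition. No separate covariate set is given for the ZBI.
- **Missing-data methods** (same section): the half rule for unanswered items, a joint model of patient and proxy QOL-AD, and joint models of outcome and time to drop-out.
- **Who is enrolled and how** (Aim 1, Participants): in severe dementia, family caregivers "may be included even if the patient has communication limitations in order to obtain data relevant to these highly vulnerable and underrepresented patients". Study Settings/Recruitment offers "providing baseline and/or follow-up study visits at participant homes or by telehealth". Appendix 1 adds: "Data collection for all study visits can be done by phone, online survey, via telehealth, or in person".

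**The concern.** These covariates are baseline values and the model has no visit-specific substitute for them. One missing value therefore removes the participant from the likelihood at baseline and at 3, 6, 9 and 12 months, not just at one visit. Outcome data already collected on a randomised participant would be discarded. For the ZBI, the lost data could belong to a caregiver who answered everything.

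The gaps are unlikely to fall at random across patients. Proxy reporting is described for the QOL-AD and the ESAS-PD, but no proxy version of the HADS or MoCA is described. Appendix 1 lists the UPDRS motor scale and MoCA as clinician-administered, and a motor examination cannot be scored over the telephone. The Innovation section says patients with dementia are included on purpose, and the Aim 1 analysis plans a dementia subgroup. Aim 3a starts from the Aim 1 models. The exclusion would carry into both unless the plan says otherwise.

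**Working it through.** **Step 1. Does any planned method rescue a wholly missing covariate?**

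- The half rule completes a scale when some items are missing. It cannot act on a scale with no items.
- The joint patient and proxy model supplies information on missing QOL-AD values, which are outcomes.
- The joint drop-out models address missing follow-up.
- Baseline QOL-AD and ZBI are modelled as outcomes, so a missing baseline score alone does not exclude anyone.

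None of these covers a wholly missing UPDRS, MoCA or HADS score.

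**Step 2. Reproduce the plan's power figures.** Inputs from Aim 1, Sample Size and Power Considerations: 125 per arm after allowing 25 losses per arm, 0.42 SD for the t-test, 110 dyads per arm at 0.44 SD for the ZBI, and 0.36 SD for the longitudinal 6-month contrast with repeated-measures correlation 0.5. Alpha is 0.05, taken as two-sided because the plan does not say.

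Power comes from the noncentral t distribution with 2n − 2 degrees of freedom and noncentrality d√(n/2).

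- QOL-AD, t-test: 0.42 × √62.5 = 3.32, power 91.1%.
- ZBI, t-test: 0.44 × √55 = 3.26, power 90.1%.
- Longitudinal 6-month contrast: residual variance 1 − 0.5² = 0.75, so the standardised effect is 0.36/√0.75 = 0.416. Then 0.416 × √62.5 = 3.29, power 90.6%.

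All three agree with the plan's 90%.

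**Step 3. Remove an assumed share m of participants for missing covariates.** The documents give no rate, so 5% to 15% is an assumption. Sample sizes are rounded down, for example 125 × 0.85 = 106.25, taken as 106.

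| m | n per arm | t-test, 0.42 SD | Longitudinal, 0.36 SD | Detectable by t-test at 90% | ZBI dyads per arm | ZBI t-test, 0.44 SD |
|---|---|---|---|---|---|---|
| 0% | 125 | 91.1% | 90.6% | 0.412 SD | 110 | 90.1% |
| 5% | 118 | 89.5% | 88.9% | 0.424 SD | 104 | 88.5% |
| 10% | 112 | 87.9% | 87.2% | 0.435 SD | 99 | 86.9% |
| 15% | 106 | 86.1% | 85.4% | 0.447 SD | 93 | 84.7% |

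The ZBI columns assume that a patient-level gap removes the caregiver. At 20% the dyads fall to 110 × 0.80 = 88, below the plan's own minimum of 90.

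**Step 4. Illustrate the change in population.** Suppose, purely hypothetically, that retained patients have an effect of 0.42 SD and excluded patients have none. With 10% excluded, the effect in all randomised patients is 0.90 × 0.42 = 0.378 SD, while the analysis still estimates 0.42 SD. If excluded patients had half the effect, it would be 0.378 + 0.10 × 0.21 = 0.399 SD.

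**The case against.** The strongest reply is that the gaps may be rare. The dementia stratum uses the MoCA (Randomization), so some cognitive assessment precedes allocation. Home visits are offered alongside telehealth. The Human Subjects section on potential benefits promises every participant a neurological examination and screening for dementia and depression. Secondary Outcome Measures expects proxy answers for impaired patients generally. A partly scored video examination may fall under the half rule. All of this stands, and it lowers the likely frequency. It does not supply a rule for when a covariate is wholly missing.

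The power loss is also modest. At 0.42 SD, the longitudinal 6-month contrast with 106 per arm still has about 94% power: 0.42/√0.75 × √53 = 3.53. Step 3 also takes covariate losses off the 125 as if none of these patients were among the 25 losses already allowed. Any overlap makes the effect smaller.

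A reader might infer three stronger points that the documents do not support:

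- **That patients with severe dementia or a remote baseline will be dropped as groups.** No section says they will lack covariates, or how many might. Those with complete covariates stay in.
- **That the rule contradicts the stated analysis principle.** The sentence "The primary analysis will use intent-to-treat" concerns crossover and is set against analysis by treatment received and by adherence. It does not address covariate completeness.
- **That a caregiver's ZBI is certainly lost when the patient cannot complete the HADS.** The HADS is collected from both patient and caregiver, and the plan does not say whose depression score enters the ZBI model.

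**Conclusion.** The point holds as a gap with a bounded effect. As written, the plan excludes randomised participants with observed outcomes whenever a baseline covariate is wholly missing. It does not depend on the MoCA, whose place in the model is unclear, because depression and disease severity appear in both covariate lists.

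The cost in power is about 2 to 5 percentage points under the assumed 5% to 15% loss: 91% to about 89% to 86% for the t-test, and about 91% to 89% to 85% for the longitudinal contrast at 0.36 SD. The cost in interpretation may be larger, because the excluded patients are likely to come disproportionately from those the trial set out to include. Its size cannot be derived from the documents.

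Bias between arms should not be inferred. If the covariates are measured before randomisation, their missingness cannot depend on the arm. The documents imply that timing but do not state it outright for the HADS and UPDRS.

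**What to change.** Replace the condition in Aim 1, Statistical Analysis, with:

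> All randomised participants with at least one observed value of the outcome are included. A missing covariate measured before randomisation is replaced by the overall mean, computed without regard to arm, with a missing-value indicator; no participant or caregiver is excluded for a missing covariate.

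The pre-randomisation condition matters, because it is what protects the treatment comparison. Mean plus indicator is one of several acceptable methods. What matters is that one is fixed in advance.

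In addition:

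- keep the complete-covariate model as a sensitivity analysis;
- reconcile the two covariate lists, so that it is clear whether the MoCA is in the model;
- state whose HADS depression score enters the ZBI model.

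The cost is a few lines of text and some indicator columns, with no new data. Covariate adjustment will explain slightly less variance for participants with a filled-in value.
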